7.4.1 Population analysis of pharmacokinetic variables

The relationship between PK and selected efficacy and/or safety endpoints may be assessed, as deemed appropriate. Results will be reported separately from the CSR.

The pharmacokinetic, demographic, safety and tumour response data collected in this study may also be combined with similar data from other studies and explored using population

pharmacokinetic and/or pharmacokinetic methods. The results of any such analyses will be reported separately from the CSR.

7.5 Calculation or derivation of tumour response variables

At each visit patients will be programmatically assigned a RECIST visit response of CR, PR, SD or PD depending on the status of their disease compared to baseline and previous assessments.

Progression of TLs will be calculated in comparison to when the tumour burden was at a minimum (ie, smallest sum of diameters previously recorded on study). In the absence of progression, tumour response (CR, PR, SD) will be calculated in comparison to the baseline tumour measurements obtained before starting treatment.

If a patient has had a tumour assessment, which cannot be evaluated, then the patient will be assigned a visit response of not evaluable (NE) unless there is evidence of progression in which case the response will be assigned as PD.

7.5.1 **Objective response**

A visit response of CR is defined when all TL and NTL lesions present at baseline have disappeared (with the exception of lymph nodes which must be <10 mm to be considered non-pathological) and no new lesions have developed since baseline. A visit response of PR is defined when the sum of diameters of the TLs has decreased by 30% or more compared to baseline (with no evidence of progression) and the NTLs are at least stable with no evidence of new lesions. A confirmed response of CR/PR means that a response of CR/PR is recorded at one visit and confirmed by repeat imaging at least 4 weeks later with no evidence of progression between confirmation visits.

In the case of stable disease, measurements should have met the stable disease criteria for a minumum interval of 5 weeks (6 weeks minus the 7-day visit window) following the start of treatment.

When the investigator is in doubt as to whether progression of disease has occurred and therefore reassesses the patient at a later date, the date of the initial scan should be declared as the date of progression if the repeat scans confirm progression.

7.5.2 Change in tumour size

Tumour size is defined as the sum of the lengths of the longest diameters of the RECIST 1.1 target lesions. Percentage change in tumour size will be determined for patients with measurable disease at baseline and is derived at each visit by the percentage change in the sum of the diameters of TLs compared to baseline.

For further details see Appendix F of this Clinical Study Protocol.

Table 5

7.6 Description of analysis sets

The analysis of data will be based on different subsets according to the purpose of the analysis. Throughout the safety results sections, erroneously treated patients (eg, those assigned to receive dose A who actually received dose B, those who failed to meet the selection criteria) will be accounted for in the actual dose group received.

Analysis Set Definition Full analysis set All patients who received at least 1 dose ofAZD9291. Safety data summaries and analyses will be produced based on the full analysis set. Pharmacokinetics Patients in the Safety Analysis PK analysis Set who have at least one measurable PK concentration, supported by the relevant date and time of this sample and for each time a PK sample was taken the dosing data for that day; and for samples taken after multiple dosing the dosing data for the 2 days prior to the sample day as well as the sample day, and have no important protocol deviations (e.g co-meds) or AEs that may impact PK. For any individual sample to be included in the PK analysis set the full sample data and dosing data needs to be present for that sample. **Evaluable for response** Dosed patients with a baseline RECIST assessment.

Analysis sets are presented in Table 5

Analysis sets

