5.2.1 Toxicity management

If a patient experiences a CTCAE grade 3 or higher and/or unacceptable toxicity (any grade) not attributable to the disease or disease-related processes under investigation, where the Investigator considers the AE of concern to be specifically associated with AZD9291, dosing will be interrupted and supportive therapy administered as required in accordance with local practice/guidelines.

In cohort 1, if the toxicity resolves or reverts to \leq CTCAE grade 2 within 3 weeks of onset, treatment with AZD9291 may be restarted at the same dose. In cohort 2, if the toxicity resolves or reverts to \leq CTCAE grade 2 within 3 weeks of onset, treatment with AZD9291 may be restarted at the same dose (80 mg) or a lower dose (40 mg) using the rules below for dose modifications (Table 1) and with discussion and agreement with the AstraZeneca Study Team Physician as needed. There will be no individual modifications to dosing schedule in response to toxicity, only potential dose reduction or dose interruption.

If the toxicity does not resolve to \leq CTCAE grade 2 after 3 weeks, then the patient should be withdrawn from the study and observed until resolution of the toxicity.

Starting Dose	Reduced AZD9291 Dose
80 mg daily	40 mg daily
40 mg daily	no dose reduction

Table 1Dose interventions

On resolution of toxicity within 3 weeks:

• If an AE subsequently requires dose interruption, AZD9291 may restart at the same dose or the reduced dose (as per Table 1), on resolution/improvement of the AE at the discretion of the Investigator.

If new or worsening pulmonary symptoms (eg, dyspnoea) or radiological abnormality suggestive of interstitial lung disease is observed, an interruption in study treatment dosing is recommended, and the AstraZeneca study physician should be informed. A questionnaire regarding the results of the full diagnostic workup (including high-resolution computed tomography (HRCT), blood and sputum culture, haematological parameters) will be sent to Investigators. It is strongly recommended to perform a full diagnostic workup, to exclude

alternative causes such as lymphangitic carcinomatosis, infection, allergy, cardiogenic edema, or pulmonary hemorrhage. In the presence of confirmatory HRCT scans where other causes of respiratory symptoms have been excluded, a diagnosis of interstitial lung disease should be considered and study treatment permanently discontinued.

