6.5 Pharmacokinetics

6.5.1 Collection of pharmacokinetic samples

Venous blood samples for determination of concentrations of AZD9291 and its metabolites (AZ5104 and AZ7550) in plasma will be taken at the times presented in Table 4. Discussions will be required with the AZ PK representative as to any effect on the PK sample schedule if dose interruption occurs within 3 days of PK sampling. The date and time of collection of each sample and the date and time of dose will be recorded.

Time relative to Dose	Single Dosing Cycle 0						ple Dos	Multiple Dosing Cvcle 2			
	D1	D2	D3	D4	D6	D1	D8	D9 (pre- dose)	D15 (pre- dose)	D1	D2 (pre- dose)
Pre-dose	X					X	X		Х	X	
0.5h	X						X				
1h	X						Х			X	
1.5h	X						Х			X	
2h	Х						Х			Х	
3h	Х						Х				
4h	X						Х			X	
6h	X						Х			X	
8h	X						Х			Х	
10h	X						X			X	
12h	X						Х			X	
24h		Х						X			Х
48h			X								
72h				X							
120h					X						

Table 4PK blood sample schedule

A 5 min window will be allowed for samples taken at 1h; a 10 min window for samples taken at 1.5-10h; a 1h window for samples taken at 12h and 24h, a 2h window at 48h-72h and a 24h window at 120h.

The timing of the pharmacokinetic samples may be adjusted during the study, dependent on emerging data, in order to ensure appropriate characterisation of the plasma concentration time profiles. The total number of samples and the total volume of blood taken from each patient will not exceed that detailed in Section 6.6.1. Residual samples may be analysed for exploratory biomarkers.

Samples will be collected, labeled, stored and shipped as detailed in the Laboratory Manual.

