The maximum plasma concentration (C_{max}), the C_{max} at steady state ($C_{ss max}$), the time of maximum concentration (t_{max}) and the t_{max} at steady state ($t_{ss max}$) will be determined by inspection of the concentration-time profiles. Where possible the terminal elimination rate constant (λ_{z}) will be calculated by log-linear regression of the terminal portion of the concentration-time profiles where there are sufficient data and the terminal half-life $(t_{\nu_{\lambda}z})$ will be calculated as $\ln 2/\lambda_z$. The area under the concentration-time curve up to the last quantifiable sample (AUC_(0-t)) and the area under the concentration-time curve up to 24 hours (AUC₍₀₋₂₄₎) will be calculated using the linear up log down trapezoidal rule. Where appropriate, the AUC(0-t) will be extrapolated to infinity using λz to obtain AUC. The area under the concentration-time curve across the dosing interval, AUCss will be calculated using the linear up log down trapezoidal rule. The apparent clearance (CL/F following the single dose and CLss/F following multiple dosing) will be determined from the ratio of dose/AUC or dose/AUCss. The volume of distribution (Vss/F or Vz/F) will be determined from the mean residence time (MRT) x CL/F and/or the accumulation ratio (RAC) will be calculated as the ratio of the AUC(0-24) on Cycle 2 Day 1 and Cycle 0 Day 1. The time dependency of the pharmacokinetics on multiple dosing will be assessed by the calculation of the ratio of AUC(0 -24) Cycle 2 day 1/AUC Cycle 0 Day 1.

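### R_AC and time dependency carry no dose term although 80 mg patients may restart at 40 mg before Cycle 2 Day 1, and Table 5 does not require steady dosing before a steady-state profile

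*Protocol*

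**What the plan says.** **Formulas (Protocol 7.4).** The accumulation ratio R_AC "will be calculated as the ratio of the AUC(0-24) on Cycle 2 Day 1 and Cycle 0 Day 1". Time dependency is assessed by "the calculation of the ratio of AUC(0 -24) Cycle 2 day 1/AUC Cycle 0 Day 1", where the denominator is the single-dose AUC to infinity. Neither contains the dose. Apparent clearance does: it "will be determined from the ratio of dose/AUC or dose/AUCss". Section 7.1 lists R_AC, time dependency, AUCss, Css,max, Css,min and CLss/F among the primary endpoints.

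**Dosing that may precede Cycle 2 Day 1 (Protocol 5.2.1).** After a toxicity interruption, if recovery comes "within 3 weeks of onset, treatment with AZD9291 may be restarted at the same dose" (cohort 1). For cohort 2 the text reads "treatment with AZD9291 may be restarted at the same dose (80 mg) or a lower dose (40 mg"). Table 1 gives 80 mg a reduced level of 40 mg and gives the 40 mg cohort none.

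**Who enters the PK set (Protocol 7.6, Table 5).** The requirement is "for samples taken after multiple dosing the dosing data for the 2 days prior to the sample day as well as the sample day". The same sentence requires that patients "have no important protocol deviations (e.g co-meds) or AEs that may impact PK". The next sentence asks for complete sample and dosing data for each individual sample.

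**Review of missed doses.** Under the heading on assessment timing when dosing is interrupted, Section 5.2 sends any missed Cycle 1 dose to the sponsor's study physician or the site monitor for advice on evaluability and PK timing. Section 6.5.1 calls for a discussion of the sampling schedule "if dose interruption occurs within 3 days of PK sampling".

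**Grouping (Protocol 7.7).** PK is summarised by dose level. AEs of dose-modified patients go to the initial dose group; for PK the level is not stated.

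**The concern.** The two ratios are meant to show how far exposure builds up on repeated dosing, and whether clearance changes with time. Both readings assume the same dose in numerator and denominator. If the dose was halved between the two occasions, a low ratio reflects the dose change and can be mistaken for low accumulation or for time-dependent PK.

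The second issue is what counts as a steady-state profile. The protocol gives the steady-state label only to Cycle 2 Day 1, nominally after 21 daily doses. It gives Cycle 1 Day 8 parameters, after 7 daily doses, no such label. Yet Table 5 would let a Cycle 2 Day 1 profile taken on the third dose after an interruption enter as AUCss, provided the dosing records are complete and nobody excludes it. An interruption that follows Section 5.2.1 is not a protocol deviation, and the AE behind it need not itself alter PK.

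At stake are primary endpoints summarised in about 12 patients per dose, where one or two wrong values can be seen in the geometric mean, the CV and the reported minimum.

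**Working it through.** The protocol states no half-life, no expected R_AC and no precision target, so there is no figure of its own to reproduce.

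**Inputs**
- Formulas for R_AC, time dependency and CLss/F: Section 7.4.
- Possible change from 80 to 40 mg: Section 5.2.1, Table 1.
- Once-daily dosing, interval 24 h: Section 5.2.
- About 12 patients per cohort: Section 7.2.
- Assumptions: linear one-compartment PK with superposition; half-life t from 12 to 72 h; k = ln 2 / t.

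**Step 1. Dose halved, patient at the new steady state.** The AUC(0-24) at steady state is dose/CL, and so is the single-dose AUC to infinity (F omitted throughout).
- Time dependency: (40/CL) / (80/CL) = 0.50; the true value is 1.
- R_AC: (40/CL) / [80(1 - exp(-24k))/CL] = 0.50 × 1/(1 - exp(-24k)), which is 0.50 of the true R_AC.
- CLss/F: 40/(40/CL) = CL, so it is unbiased when the actual dose is used.

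The half-life cancels in each comparison with the true value.

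**Step 2. Effect on a geometric mean of 12.** One patient: 0.50^(1/12) = 0.944, or -5.6%. Two patients: 0.50^(2/12) = 0.891, or -10.9%.

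**Step 3. Restart at the same dose, profile on the third dose.** After complete washout, AUCtau/AUCss = 1 - exp(-3 × 24k) = 1 - 2^(-72/t), and CLss/F is multiplied by the inverse. A second case takes 12 daily doses, then 7 dose-free days, then the third dose after restart.

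| Assumed half-life (h) | 12 | 24 | 36 | 48 | 72 |
|---|---|---|---|---|---|
| AUCtau/AUCss, complete washout | 0.98 | 0.88 | 0.75 | 0.65 | 0.50 |
| CLss/F relative to true, complete washout | 1.02 | 1.14 | 1.33 | 1.55 | 2.00 |
| AUCtau/AUCss, 7 days off | 0.98 | 0.88 | 0.76 | 0.68 | 0.59 |

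R_AC and time dependency fall by the same factor as AUCtau.

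**Step 4. Reduction from 80 to 40 mg without a gap, profile on the third 40 mg dose.** Residual drug from 80 mg raises the AUC, so CLss/F relative to true is 1/(1 + 2^(-72/t)): 0.98, 0.89, 0.80, 0.74 and 0.67 for the same half-lives. The error runs the other way from Step 3.

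**Step 5. Does dose normalisation alone repair both problems?** In Step 1 it does: 0.50 × 80/40 = 1.00. For a restart at 40 mg after complete washout, the dose-normalised ratio on the third dose is still 0.98 to 0.50, the first row of the table. The second problem needs its own rule.

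**The case against.** The protocol does have safeguards. Cycle 2 Day 1 nominally follows the 21 days of Cycle 1 directly, and Section 5.2 refers every missed Cycle 1 dose for advice on evaluability and PK timing. Section 6.5.1 adds a second review and allows sampling times to be adjusted. Table 5 excludes relevant deviations and AEs, and parameters are derived only where possible. A reader should therefore not infer that a just-restarted patient automatically counts as steady state. But these reviews are case by case and state no criterion, and none of them touches the ratio formulas.

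Several stronger readings are tempting and are not supported:
- That the 2-day look-back in Table 5 contradicts the 3-day window in Section 6.5.1. The first is a data-completeness condition, the second triggers a discussion of sampling. They serve different purposes.
- That missing dose normalisation also biases CLss/F. It does not; CLss/F errs only when sampled too early, and in either direction (Steps 3 and 4).
- That one event on Cycle 2 Day 1 certainly discards the patient's single-dose profile. The deviation and AE clause can be read per patient, but the next sentence works per sample. The wording is unclear and no more than that.
- That the restart error is always large. At 12 h it is about 2%, and shorter gaps leave residual drug.

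Exposure is also narrow. Only cohort 2 can be reduced, and escalation from 40 to 80 mg requires at least 6 months on 40 mg, long after PK sampling. Section 3.2 reports no dose-limiting toxicities in the 21-day evaluation period of the earlier study's escalation cohorts, which argues against many early reductions. Section 7.7 nevertheless plans a separate count of Cycle 1 interruptions and reductions, so such cases are foreseen.

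Parameter-level evaluability rules may be in an SAP that is not shown. That answers part of the second issue. It does not answer the first, because Section 7.4 itself states the formulas.

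**Conclusion.** The point holds at moderate severity; it is not a must-fix. The firm part is the formula: with linear PK, a cohort 2 patient reduced to 40 mg and at the new steady state by Cycle 2 Day 1 contributes half the true R_AC and half the true time-dependency ratio, irrespective of half-life.

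The second part is conditional. Table 5 can admit a profile that is not at steady state, and its error depends on an assumed half-life, on the length of the gap and on how the discretionary reviews turn out. Over 12 to 72 h with complete washout, AUCss is understated by 2% to 50% and CLss/F overstated by 2% to 100%; after a direct reduction CLss/F is understated instead.

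The documents do not say how many patients would be affected, so the one-in-12 and two-in-12 shifts are illustrations, not forecasts. The analysis is descriptive, and a careful reader of the individual data could spot such a patient, but the summary statistics would still be wrong.

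**What to change.** Amend Sections 7.4, 7.6 and 7.7, or the SAP where it governs:

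1. Compute R_AC and time dependency from dose-normalised AUC (AUC divided by the dose actually taken), or leave dose-changed profiles out of these two ratios.
2. Use Cycle 2 Day 1 for AUCss, Css,max, Css,min, CLss/F, R_AC and time dependency only after a pre-specified, fixed number of days of uninterrupted dosing at one dose. Set the number from the longest half-life among parent and metabolites. The share of steady state after n doses following washout is 1 - 2^(-24n/t); seven doses give 0.96, 0.91 and 0.80 at 36, 48 and 72 h. Do not use each patient's own Cycle 0 lambda_z: that would tie inclusion to a primary PK outcome, and lambda_z is obtained only where possible.
3. Apply exclusions per profile, so that a valid Cycle 0 profile is kept when Cycle 2 Day 1 is not usable.
4. State the dose level under which a reduced patient's PK is summarised.

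The cost is wording, settled before the PK database lock; dosing dates and changes are already recorded. The downside is possibly one or two fewer steady-state profiles. No clinical dosing rule changes.

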7.7 Methods of statistical analysis

The statistical analyses will be performed by or other designated third party providers, under the direction of the Biostatistics Group, AstraZeneca.

Demographic data

Characteristics of the patients, including medical history and disease characteristics at baseline will be listed for each patient and summarised by dose group.

Reasons for discontinuation of investigational product will be listed including the study day of treatment discontinuation and will be summarised by dose group.

Exposure

Exposure to investigational product ie, total amount of study drug received will be listed for all patients.

Total exposure and total time on study (date of last dose minus date of first dose) will be summarised by the following: mean, standard deviation, minimum, maximum, median and number of observations. In addition, the number and percentage of patients with at least one dose interruption/dose delay and at least one dose reduction will be presented separately for the initial period defined as 21 days of multiple dosing (cycle 1) and for any time following this initial period of the study.

Safety

Safety data will not be formally analysed. All patients who receive at least one dose of AZD9291 will be included in the assessment of the safety profile (safety analysis set). At the end of the study, appropriate summaries of all safety data will be produced, as defined below.

Data from all cycles of initial treatment will be combined in the presentation of safety data. AEs will be listed individually by patient and dose group. For patients who have a dose modification, all AEs (due to drug or otherwise) will be assigned to the initial dose group. The number of patients experiencing each AE will be summarised by the Medical Dictionary for Regulatory Activities (MedDRA) system organ class, MedDRA preferred term and CTCAE grade. The number and percentage of patients with adverse events in different categories (eg, causally related, CTCAE grade \geq 3 etc) will be summarised by dose group, and events in each category will be further summarised by MedDRA system organ class and preferred term, by dose group. SAEs will be summarised separately if a sufficient number occur.

Any AE occurring before the first dose of investigational product (ie, before study Day 1) will be included in the data listings but will not be included in the summary tables of adverse events.

Any AE occurring within the defined 28 day follow-up period after discontinuation of investigational product will be included in the AE summaries. Any adverse events in this period that occur after a patient has received further therapy for cancer (following discontinuation of investigational product) will be flagged in the data listings. AEs occurring after the 28 day follow-up period after discontinuation of investigational product will be listed separately, but not included in the summaries.

Haematology, clinical chemistry, vital signs, ECG data, ophthalmic examination data, demographic data and concomitant medications will be listed individually by patient and suitably summarised. For all laboratory variables, which are included in the current version of CTCAE, the CTCAE grade will be calculated. Summary statistics of mean, median, standard deviation, minimum, maximum and number of observations will be used.

Details of any deaths will be listed for all patients.

Any qualitative assessments will be summarised for all patients using the number of patients with results of negative, trace or positive.

Graphical presentations of safety data will be presented as is deemed appropriate. This may include, but is not restricted to, presentation of parameters against time, concentration or shift plots. Appropriate scatter plots will also be considered to investigate trends in parameters compared to baseline.

Pharmacokinetics

Plasma concentrations of AZD9291, AZ5104 and AZ7550 will be summarised by nominal sample time. Plasma concentrations and derived PK parameters will be summarised by dose level. Parameters following single and multiple dosing will be summarised separately. Plasma concentrations at each time point will be summarised according to dose by the following summary statistics:

- The geometric mean (gmean, calculated as $\exp [\mu]$, where μ is the mean of the data on a logarithmic scale)
- Coefficient of variation (CV, calculated as $100 \sqrt{[exp(s2)-1]}$, where s is the standard deviation of the data on a log scale)
- Gmean \pm standard deviation (calculated as exp[$\mu \pm$ s])
- Arithmetic mean calculated using untransformed data
- Standard Deviation calculated using untransformed data
- Minimum
- Maximum
- Number of observations

The following summary statistics will be presented for AUC, $AUC_{(0-24)}$, $AUC_{(0-t)}$, AUC_{ss} , C_{max} , $C_{ss max}$, $C_{ss min}$, CL/F, CL_{ss}/F , volume of distribution, $t_{\nu_{2}\lambda_{Z}}$, R_{AC} , time dependency, lambda_z, R-square, % AUC extrapolated, MRC_{max} and MRAUC:

- Gmean, calculated as $exp[\mu]$, where μ is the mean of the data on a logarithmic scale)
- CV, calculated as $100 \sqrt{[\exp(s_2)-1]}$, where s is the standard deviation of the data on a log scale)
- Arithmetic mean calculated using untransformed data
- Standard deviation calculated using untransformed data

- Minimum
- Maximum
- Number of observations

The following summary statistics will be presented for t_{max} and t_{max ss}:

- Median
- Minimum
- Maximum
- Number of observations

The following summary statistics will be presented for MRT:

- Arithmetic mean
- Standard deviation
- Median
- Minimum
- Maximum
- Number of observations

The pharmacokinetic data for AZD9291, AZ5104 and AZ7550 after a single-dose and separately, at steady state will also be displayed graphically. Displays will include plasma concentration patient profiles (on the linear and log-scale) versus time and gmean concentration (+/-standard deviation) versus time, stratified by dose.

Scatter plots of PK parameters versus dose, or log-dose will also be considered following both single and multiple dose administration of AZD9291 to visually inspect dose proportionality.

Tumour response

The analysis population for objective tumour response will be the "evaluable for response" population.

Tumour response data will be listed and if appropriate using the following response categories: Complete Response (CR), Partial Response (PR), Stable Disease (SD), Progressive Disease (PD) and Non-Evaluable (NE).

